Appendix 1 WOMAC

WOMAC OSTEOARTHRITIS INDEX VERSION VA3.1

INSTRUCTIONS TO PATIENTS

In Sections A, B, and C questions are asked in the following format. Please mark your answers by putting an “**X**” through the horizontal line.

EXAMPLES:

1. If you put your “**X**” at the left-hand end of the line as shown below, then you are indicating that you feel **no** pain.

2. If you put your “**X**” at the right-hand end of the line as shown below, then you are indicating that you feel **extreme** pain.

3. Please note:

- a) that the further to the right you place your “**X**”, the **more** pain you feel.
- b) that the further to the left you place your “**X**”, the **less** pain you feel.
- c) **please do not** place your “**X**” **past either end of the line**.

You will be asked to indicate on this type of scale the amount of pain, stiffness or disability you have felt during the last 48 hours.

Think about your _____ (study joint) when answering the questions. Indicate the severity of your pain and stiffness and the difficulty you have in doing daily activities that you feel are caused by the arthritis in your _____ (study joint).

Your study joint has been identified for you by your health care professional. If you are unsure which joint is your study joint, please ask before completing the questionnaire.

Copyright©1996 Nicholas Bellamy
All Rights Reserved

English for USA - V2

WOMAC VA3.1 QUESTIONNAIRE

WOM_A

Section A

PAIN

Think about the pain you felt in your _____ (study joint) caused by your arthritis during the last 48 hours.

(Please mark your answers with an "X".)

QUESTION: How much pain have you had . . .		Study Coordinator Use Only
1. when walking on a flat surface?	 A horizontal line with 'No Pain' at the left end and 'Extreme Pain' at the right end. A vertical tick mark is at the left end.	PAIN1 
2. when going up or down stairs?	 A horizontal line with 'No Pain' at the left end and 'Extreme Pain' at the right end. A vertical tick mark is at the left end.	PAIN2 
3. at night while in bed? (that is - pain that disturbs your sleep)	 A horizontal line with 'No Pain' at the left end and 'Extreme Pain' at the right end. A vertical tick mark is at the left end.	PAIN3 
4. while sitting or lying down?	 A horizontal line with 'No Pain' at the left end and 'Extreme Pain' at the right end. A vertical tick mark is at the left end.	PAIN4 
5. while standing?	 A horizontal line with 'No Pain' at the left end and 'Extreme Pain' at the right end. A vertical tick mark is at the left end.	PAIN5 

Copyright©1996 Nicholas Bellamy
All Rights Reserved

WOMAC VA3.1 QUESTIONNAIRE

WOM_B

Section B

STIFFNESS

Think about the **stiffness** (not pain) you felt in your _____ (study joint) caused by your arthritis during the last 48 hours.

Stiffness is a sensation of **decreased** ease in moving your joint.

(Please mark your answers with an “**X**”.)

6. How **severe** has your stiffness been **after you first woke up** in the morning?

Study Coordinator
Use Only

STIFF6 _____

7. How **severe** has your stiffness been after sitting or lying down or while resting **later in the day**?

STIFF7 _____

WOMAC VA3.1 QUESTIONNAIRE

WOM_{C1-3}

Section C

DIFFICULTY PERFORMING DAILY ACTIVITIES

Think about the difficulty you had in doing the following daily physical activities caused by your arthritis in your _____ (study joint) during the last 48 hours. By this we mean **your ability to move around and take care of yourself**. (Please mark your answers with an "x".)

QUESTION: How much difficulty have you had . . .

8. when going down the stairs?

Study Coordinator
Use Only

PFTN8 _____

9. when going up the stairs?

PFTN9 _____

10. when getting up from a sitting position?

PFTN10 _____

11. while standing?

PFTN11 _____

12. when bending to the floor?

PFTN12 _____

13. when walking on a flat surface?

PFTN13 _____

Copyright©1996 Nicholas Bellamy
All Rights Reserved

WOMAC VA3.1 QUESTIONNAIRE

WOM_{C2-3}**DIFFICULTY PERFORMING DAILY ACTIVITIES**

Think about the difficulty you had in doing the following daily physical activities caused by your arthritis in your _____ (study joint) during the last 48 hours. By this we mean **your ability to move around and take care of yourself**. (Please mark your answers with an "x".)

QUESTION: How much difficulty have you had . . .

14. getting in or out of a car, or getting on or off a bus?

Study Coordinator
Use Only

PFTN14 _____

15. while going shopping?

[figure not shown]
PFTN15 _____

16. when putting on your socks or panty hose or stockings?

[figure not shown]
PFTN16 _____

17. when getting out of bed?

PFTN17 _____

18. when taking off your socks or panty hose or stockings?

PFTN18 _____

19. while lying in bed?

PFTN19 _____

Copyright©1996 Nicholas Bellamy
All Rights Reserved

WOMAC VA3.1 QUESTIONNAIRE

WOM_{C3-3}

DIFFICULTY PERFORMING DAILY ACTIVITIES

Think about the difficulty you had in doing the following daily physical activities caused by your arthritis in your _____ (study joint) during the last 48 hours. By this we mean **your ability to move around and take care of yourself**. (Please mark your answers with an "x".)

QUESTION: How much difficulty have you had . . .

[figure not shown]
20. when getting in or out of the bathtub?

Study Coordinator
Use Only

PFTN20 _____

21. while sitting?

[figure not shown]
PFTN21 _____

22. when getting on or off the toilet?

PFTN22 _____

23. while doing heavy household chores?

PFTN23 _____

24. while doing light household chores?

PFTN24 _____

Appendix 2 Global Assessment of Disease Activity

A VAS is to be completed by the subject and the evaluating physician at time points specified in Section 7.1 for determining the Patient's and the Evaluator's Global Assessment of response to therapy score.

EVALUATOR GLOBAL ASSESSMENT (VAS SCALE)

Record your response with an “X”:

“Considering all the ways the osteoarthritis in the patient’s index knee affect him/her, what is your assessment of how much the patient’s knee is bothering him/her today?”

No pain _____ Extreme pain

PATIENT GLOBAL ASSESSMENT (VAS SCALE)

Record your response with an “X”:

Think about the pain you felt in your STUDY knee caused by your osteoarthritis during the last 24 hours.

“Considering all the ways the osteoarthritis in your STUDY index knee affects you, what is your assessment of how much your STUDY knee is bothering you today?”

No pain _____ Extreme pain

Appendix 3 EQ-5D

Under each heading, please tick the ONE box that best describes your health TODAY

MOBILITY

- I have no problems in walking about
- I have slight problems in walking about
- I have moderate problems in walking about
- I have severe problems in walking about
- I am unable to walk about

SELF-CARE

- I have no problems washing or dressing myself
- I have slight problems washing or dressing myself
- I have moderate problems washing or dressing myself
- I have severe problems washing or dressing myself
- I am unable to wash or dress myself

USUAL ACTIVITIES (e.g. work, study, housework, family or leisure activities)

- I have no problems doing my usual activities
- I have slight problems doing my usual activities
- I have moderate problems doing my usual activities
- I have severe problems doing my usual activities
- I am unable to do my usual activities

PAIN / DISCOMFORT

- I have no pain or discomfort
- I have slight pain or discomfort
- I have moderate pain or discomfort
- I have severe pain or discomfort
- I have extreme pain or discomfort

ANXIETY / DEPRESSION

[figure not shown]
- I am not anxious or depressed
- I am slightly anxious or depressed
- I am moderately anxious or depressed
- I am severely anxious or depressed
- I am extremely anxious or depressed

UK (English) v.2 © 2009 EuroQol Group. EQ-5D™ is a trade mark of the EuroQol Group

- We would like to know how good or bad your health is TODAY.
- This scale is numbered from 0 to 100.
- 100 means the best health you can imagine.
0 means the worst health you can imagine.
- Mark an X on the scale to indicate how your health is TODAY.
- Now, please write the number you marked on the scale in the box below.

YOUR HEALTH TODAY =

The best health
you can imagine

UK (English) v.2 © 2009 EuroQol Group. EQ-5D™ is a trade mark of the EuroQol Group

Appendix 4 Kellgren-Lawrence Grading Scale

Grade 1: doubtful narrowing of joint space and possible osteophytic lipping

Grade 2: definite osteophytes, definite narrowing of joint space

Grade 3: moderate multiple osteophytes, definite narrowing of joint space, some sclerosis and possible deformity of bone contour

Grade 4: large osteophytes, marked narrowing of joint space, severe sclerosis and definite deformity of bone contour

Location of Change	Original Text	Changed Text	Reason
Title Page & Throughout	Protocol version 1.0 Date 08 August 2017	Protocol version 2.0 Date 28 December 2017	Protocol revision. Cingal 16-02 amended to version 4.0
Study Synopsis	Investigational Product Cingal: A chemically cross-linked sodium hyaluronate supplied as a 4-mL unit dose with a nominal 18 mg of triamcinolone hexacetonide (TH) in a 5-mL glass syringe.	Investigational Product Subjects enrolled in Cingal 17-02 will not receive an injection. For reference only, the investigational product utilized in Cingal 16-02 was: Cingal: A chemically cross-linked sodium hyaluronate supplied as a 4-mL unit dose with a nominal 18 mg of triamcinolone hexacetonide (TH) in a 5-mL glass syringe.	Clarification that no injection performed in Cingal 17-02 trial.
Study Synopsis	Comparator Product Triamcinolone Hexacetonide (TH): 20 mg/ml supplied as 1 mL unit dose in a glass ampoule. Monovisc®: A chemically cross-linked sodium hyaluronate supplied as a 4-mL unit dose in a 5-mL glass syringe.	Comparator Product Subjects enrolled in Cingal 17-02 will not receive an injection. For reference only, the comparator products utilized in Cingal 16-02 were: Triamcinolone Hexacetonide (TH): 20 mg/ml supplied as 1 mL unit dose in a glass ampoule. Monovisc®: A chemically cross-linked sodium hyaluronate supplied as a 4-mL unit dose in a 5-mL glass syringe.	Clarification that no injection performed in Cingal 17-02 trial.
Study Synopsis	Mode of Delivery Cingal, Triamcinolone Hexacetonide, or Monovisc will be injected into the intraarticular (IA) space of the index knee using an 18-21 gauge needle.	Mode of Delivery For reference only, the mode of delivery in Cingal 16-02 was: Cingal, Triamcinolone Hexacetonide, or Monovisc will be injected into the intraarticular (IA) space of the index knee using an 18-21 gauge needle.	Clarification that no injection performed in Cingal 17-02 trial.
Study Synopsis Section 9.1	Inclusion Criteria 1. Subjects meet the inclusion criteria for Cingal 16-02 and signed the informed consent.	Inclusion Criteria 1. Only subjects that met the inclusion criteria for the Cingal 17-02 as 16-02 trial and signed the informed consent are eligible for Cingal 17-02 trial.	Clarification that only Cingal 16-02 subjects will be enrolled in Cingal 17-02 trial.
Study Synopsis Section 9.1	Exclusion Criteria Patients will not be rescreened at enrollment to Cingal 17-02 as these patients met the inclusion / exclusion criteria for the Cingal 16-02 clinical trial. All patients enrolled in the Cingal 16-02 trial will be eligible to participate in Cingal 17-02.	Exclusion Criteria Patients will not be rescreened at enrollment to Cingal 17-02 as these patients were enrolled and met the inclusion / exclusion criteria for the Cingal 16-02 clinical trial. Only patients enrolled in the Cingal 16-02 trial will be eligible to participate in Cingal 17-02.	Clarification that only Cingal 16-02 subjects will be enrolled in Cingal 17-02 trial.

	
Secondary Endpoints
 
 The change from baseline in knee pain as measured by the WOMAC Pain Score (100 mm VAS) at 39 weeks post treatment comparing the Cingal group to the TH group. The change from baseline in the Patient Global Assessment 39 weeks post treatment in the Cingal group compared to the TH group. The change from baseline in the Evaluator Global Assessment at 39 weeks post treatment in the Cingal group compared to the TH group 	
Secondary Endpoints
 
 The change from baseline in knee pain as measured by the WOMAC Pain Score (100 mm VAS) at 39 weeks post treatment comparing the Cingal group to the TH group. The change from baseline in WOMAC Physical Function score at 39 weeks post treatment comparing the Cingal group to the TH group. The change from baseline in WOMAC Stiffness score at 39 weeks post treatment comparing the Cingal group to the TH group. The change from baseline in Total WOMAC score at 39 weeks post treatment comparing the Cingal group to the TH group. 	
Exploratory Endpoints:
 
 The change from baseline in the Patient Global Assessment 39 weeks post treatment in the Cingal group compared to the TH group. The change from baseline in the Evaluator Global Assessment at 39 weeks post treatment in the Cingal group compared to the TH group. The usage of rescue medication through 39 weeks post treatment in the Cingal group compared to the TH group. 
Exploratory Endpoints:
 
 Any comparisons between groups (Cingal, Monovisc, TH), within groups and / or time points (from baseline through to 39 weeks) not described in the primary or secondary endpoints may be presented in the exploratory endpoints including: 
 ○ EuroQol (EQ-5D) ○ WOMAC Pain Score (100mm VAS) ○ OMERACT-OARSI ○ Total WOMAC ○ WOMAC Stiffness Score ○ WOMAC Physical Function ○ Patient Global Assessment ○ Evaluator Global Assessment ○ Range of Motion ○ Rescue Medication Usage ○ Number of Treatment Failures due to Additional Procedure or Use of Disallowed Medication ○ Use of Disallowed Medication
	
Study Synopsis
 
Section 7.2, 12.1.2 & 12.1.3
	
Post-Treatment Follow-Up Visits:
 
Recursent
	
Post-Treatment Follow-Up Visits:
 
Consent

	
Section 10.1
	
Post-Treatment Follow-Up Visits
	
Section 10.1
 
Post-Treatment Follow-Up Visits

			
Clarified the Cingal 17-02 Visit as a consent and not re-consent visit.
 
Clarification of 17-02 assessments

Section 17.1 & 17.2	Study Contact Information: Contract Research Organization (CRO): SynteractHCR [name] Carlsbad, CA 92008 USA	Study Contact Information: Contract Research Organization (CRO): SynteractHCR [name] Carlsbad, CA 92010	Change of address for CRO
------------------------	---	---	---------------------------

1.0 Introduction

This document presents the statistical analysis plan (SAP) for the Anika Therapeutics, Inc. protocol Cingal 17-02. This incorporates the data listings, summary tables, and statistical analyses. This document is based on the original final protocol and case report forms (CRFs).

2.0 Study Design

This sub-study is an extension of the ongoing Cingal 16-02 trial which is a multi-center, randomized, double-blind, parallel group, active comparator controlled trial to evaluate the efficacy and safety of a single injection of Cingal for the relief of joint pain in subjects with OA of the knee.

Subjects with OA defined as Kellgren-Lawrence (K-L) I-III in the index knee will be eligible for this study. Felson, et al 2004¹, encouraged the use of both OA symptoms and radiographic changes in the assessment of OA. This study will employ both methods to screen subjects. Structural severity will be evaluated with the K-L classification score, a composite index of the presence and severity of joint space narrowing, osteophytes, sclerosis, deformity and cysts

For the evaluation of symptomatic severity, two main domains are important. The first is pain and the second is functional impairment. Other domains often used include subject's overall assessment, ROM and performance. Domains identified by OMERACT as core variables to be used in clinical trials involving OA are pain, function and the Patient Global Assessment which will be captured as part of this study.

Baseline and post-treatment pain, physical function and stiffness will be measured using the WOMAC questionnaire. Range of Motion, Patient and Evaluator Global Assessment and the EuroQol will be used to assess symptomatic severity throughout the study. In addition, the number of acetaminophen/paracetamol pills taken will be captured as an indirect measure of pain and will be done at each visit.

Subjects meeting the inclusion/exclusion criteria will be randomized to receive a single injection of Cingal, Monovisc or triamcinolone hexacetonide (TH) in the index knee. Since there is a difference in volume between Cingal, Monovisc and TH, the treating physician will not be considered blinded. To maintain the double-blind design of the study, there will be a person assigned to the role of Treating Physician and one person assigned to the role of Blinded Evaluator. The Treating Physician, most often the PI, will administer the injection but will not participate in the evaluation of study treatment effectiveness. A second individual, designated as the Blinded Evaluator, is blinded to treatment and will complete the pre- and post-treatment Evaluator Global Assessment, knee exams and ROM measurements. To maintain the subject blinding, the injection syringe will be prepared separate from the patient and the injection will be masked from the subject.

¹ Felson, DT, Nevitt MC. Epidemiologic studies for osteoarthritis: new versus conventional study design approaches. *Rheumatic Diseases Clinics of North America* 2004; 30(4):783-97.

The subject will be trained on how to complete the WOMAC, Patient Global Assessment and EuroQol. The subject should complete these questionnaires prior to any physical evaluation that must be done at each follow-up visit.

The Blinded Evaluator will collect and record AEs from the subjects and consult the Treating Physician only as needed in the management of AEs. The Blinded Evaluator will be a physician, research nurse, registered physiotherapist or physician assistant trained to perform the assessments outlined in the protocol.

Up to 40 sites in Europe are participating in the study to enroll 576 subjects. Subject participation in this extension study will last approximately 13 additional weeks beyond the Cingal 16-02 trial with follow-up the visit scheduled at weeks 39 after the treatment injection in Cingal 16-02.

3.0 Objectives

The objective of this sub-study is to evaluate the efficacy and safety at 39 week follow up of a single injection of Cingal for relief of joint pain in subjects with OA of the knee who have not responded to conservative treatment (weight reduction, physical therapy, pain medications, etc.).

3.1 PRIMARY EFFICACY ENDPOINT

- The responder rate as identified by the Outcomes Measures for Rheumatic Arthritis Clinical Trials-Osteoarthritis Research Society International (OMERACT-OARSI) responder index at 39 weeks post treatment comparing the Cingal group to the TH group.

3.2 SECONDARY EFFICACY ENDPOINTS

- The change from baseline in knee pain as measured by the WOMAC Pain Score (100 mm VAS) at 39 weeks post treatment comparing the Cingal group to the Triamcinolone Hexacetonide (TH) group.
- The change from baseline in WOMAC Physical Function score at 39 weeks post treatment comparing the Cingal group to the TH group.
- The change from baseline in WOMAC Stiffness score at 39 weeks post treatment comparing the Cingal group to the TH group.
- The change from baseline in Total WOMAC score at 39 weeks post treatment comparing the Cingal group to the TH group.
- The change from baseline in the Patient Global Assessment 39 weeks post treatment in the Cingal group compared to the TH group.
- The change from baseline in the Evaluator Global Assessment at 39 weeks post treatment in the Cingal group compared to the TH group.
- The usage of rescue medication through 39 weeks post treatment in the Cingal group compared to the TH group.

3.3 EXPLORATORY ENDPOINTS

Any comparisons between groups (Cingal, Monovisc, TH), within groups and / or time points (from baseline through to 39 weeks) not described in the primary or secondary endpoints may be presented in the exploratory endpoints including:

- EuroQol (EQ-5D)
- WOMAC Pain Score (100mm VAS)
- OMERACT-OARSI
- Total WOMAC
- WOMAC Stiffness Score
- WOMAC Physical Function
- Patient Global Assessment
- Evaluator Global Assessment
- Range of Motion
- Rescue Medication Usage
- Number of Treatment Failures due to Additional Procedure or Use of Disallowed Medication

3.4 SAFETY ENDPOINT

The incidence, timing, severity, and relationship to treatment of all Adverse Events (AE) will be collected and coded using Medical Dictionary for Regulatory Activities (MedDRA). Local injection site and non-local events will be recorded separately.

4.0 Statistical Methods in Protocol

4.1 STATISTICAL METHODS

This Statistical Analysis Plan provides the details of the statistical analysis of the study data that is described in the protocol.

4.1.1 Sample Size

The primary comparison in the study will be between Cingal and triamcinolone hexacetonide with respect to the difference in the change in the WOMAC pain score from baseline at 26 weeks after study injection.

It is assumed that the difference in the mean responses for Cingal and triamcinolone hexacetonide at 26 weeks would be 10 mm based on previous clinical trials of similar viscosupplementation products and the Cingal 13-01 trial with a standard deviation of 20. The sample size calculation is based upon a t-test. The sample size that is necessary to detect that specified difference at a power of 90% with a significance level of 5% in a 2:1 enrollment ratio is 128 in the Cingal group and 64 in the triamcinolone hexacetonide group. If a 15% drop out rate is assumed then enrolling in a 24:4:1 (Cingal: Monovisc :triamcinolone hexacetonide ratio) a total of 576 evaluable subjects, 256 subjects in the Cingal arm, 256 subjects in the Monovisc arm and 64 subjects in the triamcinolone hexacetonide arm is needed. This will provide 90% power to detect the difference between Cingal compared to triamcinolone hexacetonide at 26 weeks at a 5% significance level.

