3 STUDY SYNOPSIS

Title	Extension Study to Cingal 16-02: Trial Extension to 39 Week Follow Up in the Randomized, Double-Blind, Active Comparator Controlled, Multi-Center Study of a Single Injection Cross-Linked Sodium Hyaluronate Combined with Triamcinolone Hexacetonide (Cingal) to Provide Symptomatic Relief of Osteoarthritis of the Knee
Study Objective	To evaluate the efficacy and safety of a single injection of Cingal for relief of joint pain at 39 week follow up in subjects with Osteoarthritis (OA) of the knee who have not responded to conservative treatment.
Investigational Product	Subjects enrolled in Cingal 17-02 will not receive an injection. For reference only, the investigational product utilized in Cingal 16-02 was: Cingal : A chemically cross-linked sodium hyaluronate supplied as a 4-mL unit dose with a nominal 18 mg of triamcinolone hexacetonide (TH) in a 5-mL glass syringe.
Comparator Product	Subjects enrolled in Cingal 17-02 will not receive an injection. For reference only, the comparator products utilized in Cingal 16-02 were: Triamcinolone Hexacetonide (TH) : 20 mg/ml supplied as 1 mL unit dose in a glass ampoule. Monovisc® : A chemically cross-linked sodium hyaluronate supplied as a 4-mL unit dose in a 5-mL glass syringe.
Mode of Delivery	For reference only, the mode of delivery in Cingal 16-02 was: Cingal, Triamcinolone Hexacetonide, or Monovisc will be injected into the intraarticular (IA) space of the index knee using an 18-21 gauge needle.
Study Design	Multi-center, randomized, double-blind, parallel group, 3-arm, active comparator controlled study
Phase	Phase III
Sample Size	A total of 576 subjects will be enrolled. This equates to 256 subjects injected with Cingal, 256 subjects injected with Monovisc and 64 subjects injected with TH. All subjects who meet enrollment criteria and completed the 26 week follow up in Cingal 16-02 will have the option to participate in the sub-study.
Study Duration	The entire sub-study duration will be an additional 13 weeks. The follow up visit will be scheduled at 39 weeks post treatment.

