12.1 Sample Size

The sample size for Cingal 16-02 was based on the primary comparison in the study between Cingal and triamcinolone hexacetonide with respect to the difference in the change in the WOMAC pain score from baseline at 26 weeks after study injection. The first secondary comparison is between Cingal and Monovisc with respect to the difference in the change in the WOMAC pain score from baseline at 3 weeks after study injection. All comparisons are made using a 5% significance level. The primary comparison is powered at 90% power and in a 2:1 randomization requires 128 patients in the Cingal group and 64 in the triamcinolone hexacetonide group. It is assumed that the difference in the mean responses for Cingal and triamcinolone hexacetonide at 26 weeks would be 10 mm based on previous clinical trials of similar viscosupplementation products [20, 21] and the Cingal 13-01 trial with a standard deviation of 20. The sample size calculation is based upon a t-test. The sample size that is necessary to detect that specified difference at a power of 90% with a significance level of 5% in a 2:1 enrollment ratio is 128 in the Cingal group and 64 in the triamcinolone hexacetonide group.

It is further assumed that the difference between Cingal and Monovisc at 3 weeks will be 5 mm and a standard deviation of 20 mm, thus it will require a minimum of 253 patients in each group to detect that difference at 80% power. With the triamcinolone hexacetonide group set at 64 patients, the number of patients in the Cingal and Monovisc groups will be increased to provide a 4: 1 randomization ratio. This will yield 256 in the Cingal group, 256 in the Monovisc group and 64 in the triamcinolone hexacetonide group. This provides a total sample size of 576 patients.

Since the primary analysis in this study is an intent to treat analysis and the missing data for a patient will be imputed using mixed effects models, no drop out rate will be assumed for this study. Thus the total sample size for Cingal 16-02 was set at 576 patients.

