4.1.2 Primary Efficacy Endpoint

4.1.2.1 The responder rate as identified by the OMERACT-OARSI responder index at 39 weeks post treatment comparing the Cingal group to the triamcinolone hexacetonide group.

The response rate for the Cingal group and Triamcinolone Hexacetonide (TH) group will be calculated and tested using Fisher's exact test. Formally, the hypothesis to be tested is:

$H_0: \pi_C = \pi_T$ versus $H_0: \pi_C \neq \pi_T$

Where π_C is the responder rate for the Cingal group and π_T is the responder rate for the triamcinolone hexacetonide group.

This will be estimated and tested using PROC FREQ with the EXACT option. The results will be displayed similar to:

Summary of the OMERACT-OARSI Responder Rates at 39 Weeks

Parameter	Cingal	Monovisc	TH
Estimate n/N (%)			
Cingal vs TH (Primary) (p-value)			

Parameter	Cingal	Monovisc	TH
Cingal vs Monovisc (p-value)			
Monovisc vs TH (p-value)			

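### SAP 4.1.1 gives an unlabelled 90% power for week-26 pain, which the protocol attributes to Cingal 16-02; no power is stated for the week-39 responder primary of Cingal 17-02

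*SAP*

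**What the plan says.** SAP 4.1.1 (Sample Size) opens with "The primary comparison in the study will be between Cingal and triamcinolone hexacetonide" and specifies change in WOMAC pain at week 26. It assumes a 10 mm difference and an SD of 20, derives 128 Cingal and 64 TH subjects for 90% power at 5%, and continues: "If a 15% drop out rate is assumed then enrolling in a 24:4:1 (Cingal: Monovisc :triamcinolone hexacetonide ratio) a total of 576 evaluable subjects", split 256/256/64. It ends: "This will provide 90% power to detect the difference between Cingal compared to triamcinolone hexacetonide at 26 weeks at a 5% significance level". Cingal 16-02 is not mentioned in that section.

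SAP 4.1.2, immediately after, gives the primary endpoint as "The responder rate as identified by the OMERACT-OARSI responder index at 39 weeks post treatment comparing the Cingal group to the triamcinolone hexacetonide group", tested by Fisher's exact test. SAP 3.1 and Protocol 7.1 and 12.1.1 name the same endpoint.

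Protocol 12.1 carries the same 128/64 calculation but attributes it: "The sample size for Cingal 16-02 was based on the primary comparison in the study between Cingal and triamcinolone hexacetonide". It adds a week-3 comparison of Cingal with Monovisc (5 mm, SD 20), for which "it will require a minimum of 253 patients in each group to detect that difference at 80% power". It then sets those two arms at four times the 64 in the TH arm, and says that "no drop out rate will be assumed for this study". The protocol synopsis says "A total of 576 subjects will be enrolled" and, in the same entry, describes the arms as subjects injected. It makes the sub-study optional for those who completed 26 weeks. The Protocol Introduction gives the randomisation as 4:4:1.

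**The concern.** The SAP names two different primary comparisons in consecutive sections and attaches power only to the one that this trial does not test. Endpoint, week and test all differ. Someone working from the SAP alone could take 90% as the power of the 17-02 primary. That matters most if the result is not significant: a null Fisher test could be over-read as evidence of no difference because the trial appears to have been powered at 90%.

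The explanation of 576 is also unreliable. Drop-out is 15% in one document and none in the other. The 576 are evaluable in SAP 4.1.1 but enrolled in SAP 2.0 and the protocol synopsis. The ratio does not match the arm sizes printed beside it.

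**Working it through.** **Inputs.** Difference 10 mm, SD 20, 5% level, 128/64 and 256/256/64 (SAP 4.1.1). Week 3: 5 mm, SD 20, 253 per group (Protocol 12.1). Two-sided testing is read from the not-equal alternatives. Neither document gives a responder rate, so TH rates of 40 to 80% are my assumption.

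**1. The plan's own figure.** Two-sample t-test, noncentrality δ = d / (SD × √(1/n₁ + 1/n₂)), n₁ + n₂ − 2 degrees of freedom, two-sided 5%.

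| Comparison | n₁/n₂ | δ | Power |
|---|---|---|---|
| Week-26 pain, 10 mm | 128/64 | 3.266 | 90.1% |
| Week-26 pain, 10 mm | 256/64 | 3.578 | 94.6% |
| Week-26 pain, 10 mm, after 15% loss | 218/54 | 3.289 | 90.6% |
| Week-3 pain, 5 mm | 253/253 | 2.812 | 80.1% |

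The 128/64 figure reproduces. The third row uses 256 × 0.85 = 217.6 and 64 × 0.85 = 54.4.

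**2. Evaluable or enrolled.** If 576 are evaluable after 15% loss, 576 / 0.85 = 677.6, so about 678 would have to be randomised. If 576 are randomised, 576 × 0.85 = 489.6, so about 490 remain. Both readings cannot hold. The SAP's 90% together with 15% loss fits the second.

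**3. Origin of 256.** In Protocol 12.1 it is 4 × 64 = 256, which meets the week-3 minimum of 253. Since 256 / 253 = 1.012, on that basis the arms hold no 15% allowance.

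**4. Ratio.** 24:4:1 applied to 576 gives about 477/79/20. 4:4:1 gives exactly 256/256/64, the sizes that the SAP prints.

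**5. The week-39 primary.** Two-sided Fisher's exact test at 5%. Power is the sum, over all pairs of responder counts with Fisher p ≤ 0.05, of Bin(x; n_C, π_C) × Bin(y; n_T, π_T), fully enumerated.

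| Assumed TH rate | Power for +10 points, 256/64 | Points for 80% power, 256/64 | Points for 90% power, 256/64 | Points for 80% power, 218/54 |
|---|---|---|---|---|
| 40% | 27.6% | 19.8 | 22.7 | 21.3 |
| 50% | 28.8% | 19.6 | 22.3 | 21.2 |
| 60% | 30.7% | 18.1 | 20.6 | 19.6 |
| 70% | 37.8% | 16.0 | 18.1 | 17.3 |
| 80% | 52.5% | 13.1 | 14.6 | 13.9 |

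The 256/64 columns assume complete week-39 data. The 218/54 column is a complete-case approximation; the specified primary analysis is ITT with multiple imputation (SAP 4.5), which these figures do not model.

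**The case against.** The strongest reply is that nothing operative is wrong. The 90% sentence says that it refers to week 26, the opening sentence of SAP 4.1.1 names WOMAC pain, and SAP 4.1.2 gives the correct primary. Protocol 12.1 carries the label, and Protocol 12 makes its own methodology the basis for the SAP. A reader with both documents can trace the origin. The size was fixed by 16-02, so no design decision turns on a power figure for 17-02, and any such figure rests on TH rates that the documents do not give.

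Much of this stands. It makes the point one of labelling and applicability, not of arithmetic, and it rules out asking for more patients. It does not remove the mislabelled comparison in the SAP, and the protocol is silent on power for the week-39 primary too.

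Three stronger readings are tempting, and the documents do not support them:

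- *That the trial is short of subjects for week-26 pain, or needed about 678.* That total arises only if evaluable is taken literally. With 576 randomised and 15% lost, week-26 power is still 90.6%.
- *That SAP 4.1.1 simply reproduces the 16-02 text.* The 15% drop-out and the 24:4:1 ratio are not in Protocol 12.1, and the 16-02 documents are not available to compare.
- *That randomisation was at 24:4:1.* The arm sizes in the same sentence and the Protocol Introduction both point to 4:4:1.

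**Conclusion.** The point holds and should be fixed. SAP 4.1.1 applies to Cingal 17-02, without attribution, a sample-size calculation that Protocol 12.1 assigns to Cingal 16-02. Its 90% is right for week-26 pain and says nothing about the week-39 responder primary.

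Under the assumed TH rates, 90% power for the actual primary would need about 15 to 23 points with complete data on 256 and 64 subjects, and a 10-point difference would have 28 to 53% power. These are best-case values: participation in 17-02 is optional and limited to those who completed 26 weeks, so 576 is a ceiling.

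The conflicts over drop-out and over evaluable versus enrolled are real but need only reconciliation; the ratio is a typing slip. The endpoint, test and alpha of 17-02 are unaffected.

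**What to change.** In SAP 4.1.1:

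- Label the calculation, its drop-out assumption and its 90% as belonging to Cingal 16-02, week-26 WOMAC pain. Stop describing that as the primary comparison of this study.
- Reconcile the 15% drop-out with Protocol 12.1, as a planning assumption of 16-02.
- Replace 576 evaluable with 576 randomised and injected in 16-02. The word enrolled would be ambiguous, because Protocol 2 defines it as having signed the consent form.
- Change 24:4:1 to 4:4:1.
- State that 256 per arm is 4 × 64, which meets the week-3 Cingal versus Monovisc minimum of 253 per group at 80% power.

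Add to SAP 4.1.1 and Protocol 12.1:

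> The size of Cingal 17-02 was fixed by Cingal 16-02 and was not separately powered for the week-39 primary. With at most 256/64 subjects and complete week-39 data, two-sided Fisher's exact test at 5% has 80% power for a responder difference of X points at a TH rate of Y%. Participation in 17-02 is optional, so this is a best case.

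Y should be the sponsor's own planning rate. For illustration, X is about 16 to 20 at Y = 40 to 70 and about 13 at Y = 80. Any figure for reduced attendance (at 218/54, about 17 to 21 and 14 points) should be labelled a complete-case approximation.

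The cost is wording in one SAP section and one added statement in the protocol. Sample size, endpoint, test and alpha stay as they are. The only downside is a less favourable stated power.
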